# 9.2 Definition of Serious Adverse Event

A serious adverse event is an adverse event that meets the following criteria.

- Results in death
- Is life-threatening
- Requires admission to a hospital or clinic or prolongation of the duration of the existing hospitalization
- Results in disability
- Is associated with a risk of disability
- Is medically significant in a way similar to the above
- Is a congenital anomaly or birth defect

# 9.3 Handling of Abnormal Changes in Laboratory Data

Laboratory test findings and test results that meet the following criteria (including blood tests, urinalysis, vital signs, and other test results) will be handled as adverse events.

- Suspension (or postponement of administration), or discontinuation of the study drug is necessary
- New medical or surgical intervention is necessary
- The investigator or subinvestigator determines that the finding is clinically significant for any other reason

#### 9.4 Adverse Event Collection Period

The adverse event collection period will be as follows.

- From the first dose of the study drug at each dose level in Part 1 to the end of the follow-up period
- From the first dose of the study drug in Part 2 to the end of the follow-up period
- From the first dose of the study drug in Part 2-Extension to the end of the follow-up period in Part 2-Extension-2 (for subjects participating in the study from Part 2-Extension-2, from the first dose of the study drug in Part 2-Extension-2 to the end of the follow-up period in Part 2-Extension-2. For subjects participating in the long-term extension study, until the first dose of the study drug in the long-term extension study.)

All adverse events that occur during this period will be recorded on the case report form. Even outside the collection period, adverse events that the investigator or subinvestigator determines have a relationship with the study drug will be reported to the sponsor in the same way as during the collection period.

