# 6.4.1 Items to Be Performed After Registration up to the Day Before the First Dose of Study Drug (Day 0)

These will be performed after registration up to the day before the first dose of the study drug in each subject (Day 0). These items will also be performed in subjects participating in the study from Dose Level 3 or Dose Level 4 of Part 1, Part 2, Part 2-Extension or Part 2-Extension-2

<Items performed up to 28 days before the first dose of the study drug>

- Muscle biopsy, skin biopsy\*4
- <Items performed from 14 days before the first dose of the study drug up to the day before the first dose of the study drug (Day 0)>
  - 1) Checking concomitant medications and concomitant therapy
  - 2) Height and body weight
  - 3) Vital signs and clinical findings
  - 4) Blood tests and urinalysis
  - 5) 12-lead electrocardiogram
  - 6) \*5
  - 7) Motor function assessment\*6
  - 8) Respiratory function assessment\*7
  - 9) Cardiac function assessment\*7
  - 10) Quantitative muscle strength assessment\*6
  - 11) Blood collection

- Anti-dystrophin antibody
- Anti-DS-5141b antibody
- Blood cell dystrophin mRNA\*4
- 12) Urine collection
  - Urine protein
  - Urine DS-5141b metabolites\*8
- \*4: Not necessary in subjects participating in the study from Part 2-Extension or Part 2-Extension-2.
- \*5: To be performed in subjects participating in the study from Part 2-Extension-2.
- will be performed after registration and before the first dose of the study drug.
- \*6: To be performed twice, at least 28 days after muscle biopsy.
- \*7: To be performed at least 28 days after muscle biopsy.
- \*8: Not necessary in subjects participating in the study from Part 2, Part 2-Extension or Part 2-Extension-2.

#### 6.4.2 Part 1

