# 6.9 Expression of Dystrophin Protein and Production of Exon 45-Skipped Dystrophin mRNA in Muscle Tissue (Muscle Biopsy)

To measure the dystrophin protein in muscle tissue and the dystrophin mRNA induced by exon 45 skipping, after registration, before the first dose of the study drug in each subject, after the last dose of the study drug (Day 85 to Day 99, or at withdrawal) in Part 2, after the last dose of the study drug (Week 49/ Day 337 to Week 51/ Day 351, or at withdrawal) in Part 2-Extension, and after the last dose of the study drug (Week 49/ Day 337 to Week 51/ Day 351, or at withdrawal) in Part 2-Extension-2, muscle tissue will be collected from, in principle, the biceps brachii muscle by open muscle biopsy. The location of collection will be decided after checking the condition of the muscle by MRI or CT performed in advance. After collection, the

specimen will be processed promptly, and stored frozen (set temperature:  $\leq -70^{\circ}$ C) in a container prepared by the sponsor or central laboratory until it is submitted to the clinical specimen storage facility contracted by the sponsor. Details are specified in a separate procedure.

The investigator or subinvestigator will record whether a muscle biopsy was performed, the date of biopsy, and the region of the collected muscle on the case report form.

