#### 9.1 Definition of Adverse Event

An adverse event is any untoward or unintended sign (including abnormal changes in laboratory data and abnormal changes in vital signs), symptom or disease that occurs in a subject, whether or not they have a relationship with the study drug. Symptoms or diseases that occur before administration of the study drug will be considered complications, and will not be handled as adverse events. However, if a complication worsens during administration of the study drug, it will be handled as an adverse event, and the date when worsening was observed will be considered the date of onset of the adverse event.

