#### 9.7.2 Action If a Serious Adverse Event Occurs

If a serious adverse event occurs, the investigator or subinvestigator will provide appropriate treatment, and also promptly report information about the adverse event to the sponsor, for example by telephone or fax. The investigator will also report the details in writing to the sponsor and the director of the study site. The written report to the director of the study site will be made according to the procedures and format of the relevant medical institution.

will be recorded on the case report form.

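### A complication of the required pre-dose biopsy is not an adverse event unless it worsens on drug, so even a serious one triggers no prompt report to the sponsor and enters no adverse event table

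*Combined protocol and SAP*

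**What the plan says.** **The procedure.** Section 6.4.1 lists "Muscle biopsy, skin biopsy" among the items between registration and the first dose. Section 6.9 says that "muscle tissue will be collected from, in principle, the biceps brachii muscle by open muscle biopsy" and places one such operation before the first dose in each subject. Section 6.12.2 limits the skin sample to boys entering from Part 1 or Part 2. Footnote 4 in 6.4.1 exempts extension entrants, but it is not clear whether it covers the skin biopsy only or the muscle biopsy as well.

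**The classification.** Section 9.1: "Symptoms or diseases that occur before administration of the study drug will be considered complications, and will not be handled as adverse events". It gives one exception: "if a complication worsens during administration of the study drug, it will be handled as an adverse event". Section 9.2: "A serious adverse event is an adverse event that meets the following criteria".

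**The collection period.** Section 9.4 starts "From the first dose of the study drug at each dose level in Part 1" and uses the first dose for every other entry route. Beyond that period: "Even outside the collection period, adverse events that the investigator or subinvestigator determines have a relationship with the study drug will be reported".

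**The duty to report.** For a serious adverse event, 9.7.2 requires the investigator to "promptly report information about the adverse event to the sponsor". Table 9.5-1 grades causality against the study drug only. Section 11.2.3 leaves subjects who were never dosed out of the safety population.

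**The concern.** The boys are aged 5 to under 11, and the operation is done because the protocol requires it. Section 6.1 counts a subject as on study from consent. Yet the rule in 9.1 has no exception for harm from a study procedure, so a wound infection, bleed or anaesthetic event after the baseline biopsy falls under it. This is a rule the protocol states, not a detail it leaves out.

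Two things are at stake. The sponsor has no assured prompt notice of serious harm from a procedure that it requires and that most boys will have again. The safety tables would also be silent on that harm, whatever its severity.

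**Working it through.** The plan states no figure on this point. The check is a reading of the rules together, with two small calculations.

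**1. Follow one event through the rules.** Suppose a boy has a wound infection after the baseline biopsy, is admitted to hospital, and recovers before Day 1.
- 9.1: it occurs before study drug, so it is a complication and not an adverse event. The worsening exception does not apply because it has resolved.
- 9.2: admission is one of the seriousness criteria, but the definition covers adverse events only. It is not a serious adverse event.
- 9.7.2: the prompt report is not triggered.
- 9.4: the event lies outside the period. The exception needs a relationship to the study drug, and none has been given.
- 11.4.4.1: the tables count adverse events, so it does not appear.

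If the boy is then withdrawn without being dosed, 11.2.3 removes him from the safety population. The withdrawal tests in 6.5 begin at Day 1 of a part, and the follow-up in 6.6 is timed from the last dose, so neither is defined for him.

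The same infection after the Part 2 biopsy (Day 85 to Day 99) falls in the follow-up period and is collected. Only the timing differs.

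**2. Length of the uncovered interval.** Inputs are from 6.4.1: Day 0 is the day before the first dose (Day 1). Baseline motor, respiratory, cardiac and strength assessments are due from 14 days before the first dose to Day 0, and at least 28 days after the biopsy (footnotes 6 and 7).
- Latest biopsy day: 0 − 28 = Day −28.
- Shortest gap to first dose: 1 − (−28) = 29 days.
- If the assessments are done at the start of their window: 14 + 28 = 42 days at least.
- Reading only the 28-day line for the biopsy itself, as a deadline: 28 days.

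The gap is therefore at least about 28 to 29 days, which contains the early post-operative period.

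**3. Share of planned muscle biopsies that fall before collection.** Counted from 6.9 and 6.5, with one pre-dose operation each:

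| Route | Muscle biopsies | Pre-dose share |
|---|---|---|
| Part 1 or Part 2 through both extensions | 4 | 1/4 = 25% |
| Same, without a Part 2-Extension biopsy | 3 | 1/3 = 33% |
| Entry at Part 2-Extension, through Part 2-Extension-2 | 3 | 1/3 = 33% |
| Entry at Part 2-Extension-2 | 2 | 1/2 = 50% |
| Stops after Part 2 | 2 | 1/2 = 50% |
| Withdrawn Day 16 to 64 of Part 1, biopsy done under 6.5.4 | 2 | 1/2 = 50% |
| Completes Part 1 and does not continue | 1 | 1/1 = 100% |

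The rows for extension entrants assume that 6.9 governs and that footnote 4 does not remove their baseline muscle biopsy. These are shares of operations, not rates of harm; the documents give no biopsy complication rate.

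**The case against.** **Other records exist.** A reader might infer that baseline biopsy harm leaves no record at all. The documents do not support that.
- Section 6.3 collects complications and medical history, including conditions resolved before study drug starts.
- Section 5.6 records concomitant drugs and therapies from registration, with their indication, so an antibiotic for a wound would be visible.
- Section 6.4.1 requires vital signs, clinical findings and blood tests in the 14 days before dosing.
- Section 4.3 records the reason for withdrawal and follows abnormalities seen then.
- Section 13.2 brings in the sponsor if a subject requests a response to a study-related injury.

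This stands as a limit on the claim. It does not answer it. The 6.3 item sits among pre-registration checks while the biopsy follows registration, and resolved conditions are listed at the investigator's discretion. The compensation route depends on a request. None of these routes classifies the event, grades its seriousness or requires a prompt report.

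**Few boys remain exposed.** Section 1.2.6 gives 7 subjects dosed and Part 2-Extension-2 in progress by 30 Aug 2019. The home-administration time points in 6.4.5.2 start at Week 28, which suggests that dosing was well advanced. For those boys the baseline operation is over, and the remaining one falls inside collection. This stands too, and it narrows the forward effect to subjects added under 5.8. A boy added now would probably enter at Part 2-Extension-2, with no skin biopsy and with footnote 4 in play.

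**The comparator argument.** A reader might infer that, without pre-drug events to compare with, later biopsy events will be misread as drug effects. I would not press this. Table 9.5-1 lets the investigator attribute an event to factors other than the drug, the analysis is descriptive (11.1), and about seven baseline operations would make a very weak comparator.

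**Starting at first dose is reasonable for drug incidence.** Agreed, and the change proposed here leaves that start unchanged.

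**Conclusion.** The point holds on the text. Under 9.1, 9.2, 9.4 and 9.7.2 together, a complication of the required pre-dose biopsy becomes an adverse event only if it worsens during administration. Otherwise it generates no serious adverse event report and no entry in an adverse event table, however serious it is.

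The interval concerned is about 28 to 29 days or more. The pre-dose operation is typically 1 of 2 to 1 of 4 planned, and the only one for a boy who completes Part 1 and does not continue. No single percentage fits every route. In particular, a reader might infer 100% for anyone who leaves during Part 1, but 6.5.4 lists a post-dose biopsy, as far as possible, for withdrawal on Day 16 to 64.

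The conclusion rests on 6.9 applying to each subject. If footnote 4 of 6.4.1 exempts extension entrants from the muscle biopsy, the point does not reach them. It also assumes that no rule on procedure harm stands in pages or separate procedures outside the text reviewed. The documents report no baseline biopsy harm, and nothing here implies that any occurred. The drug-event analyses themselves are not put in doubt.

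**What to change.** - **9.1 and 9.4:** state that from consent, or at latest from the pre-dose biopsy, all serious events and any event related to a study procedure are recorded, whether or not study drug has been given.
- **9.7.2:** state that it applies to these events.
- **Table 9.5-1:** add a causality item for study procedure beside the one for study drug.
- **11.4.4:** add a separate listing of pre-treatment events for all registered subjects, including those never dosed. The safety population in 11.2.3 need not change, and drug-event incidence still starts at the first dose.
- **6.4.1 and 6.9:** reconcile footnote 4 with the statement that each subject has the biopsy, so that it is clear who is covered.
- **Boys already enrolled:** look for such events in the source records and add them to the listing.

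The cost is a short amendment, one case report form item, a few more event records, one extra listing and a limited look back at source records. No endpoint, treatment or planned drug-event table changes.

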# 9.5 Items to Investigate for Adverse Events

If an adverse even occurs during the study, the items shown in Table 9.5-1 will be investigated and recorded on the case report form or another document.

Table 9.5-1 Items to Investigate When an Adverse Event Occurs

Item to investigate	Details of investigation				
Details of adverse event	Adverse event term, date of onset				
Action taken for adverse event	Details of study drug action taken, details of other action taken				
Outcome	Outcome classification, day of outcome assessment, stop date				
Outcome classification	Recovered/resolved	The adverse event disappears and the subject returns to the condition before the adverse event occurred			
	Recovering/resolving	The adverse event almost disappears, and the subject returns to a condition close to that before the adverse event occurred			
	Not recovered/not resolved	The adverse event does not disappear, and the subject remains in a condition similar to when the adverse event occurred (unchanged)			
	Recovered/resolved with sequelae	The adverse event has disappeared, but the subject has sequelae			
	Death	This indicates that the investigator etc. considers that the adverse event has a relationship with the death, or that a relationship cannot be ruled out, and in cases of death due to causes such as worsening of the underlying disease, this classification does not apply			
	Unknown	There is no information, and the outcome is unknown			
Severity	Mild	A tolerable level, with no impairment to activities of daily life			
	Moderate	A level with some impairment of activities of daily life			
	Severe	A level at which activities of daily life are impossible			
Seriousness	Serious/nonserious				
Causality	Causality classification (as per the following causality classification), reason for judgment				
Causality classification	Related	
 
There is a reasonable temporal relationship between the occurrence of the adverse event and the administration of the study drug, it is not appropriate to determine that the adverse event is due the subject's condition or factors other than the study drug (such as the underlying disease, complications or concomitant medications), and an association with the study drug cannot be ruled out
 
There is a reasonable temporal relationship between the occurrence of the adverse event and the administration of the study drug, and the adverse event can be explained as a known reaction to the study drug or similar compounds, or based on its pharmacological action
 
			
	Unrelated	
 
There is no reasonable temporal relationship between the occurrence of the adverse event and administration of the study drug, or it is
 
			

Item to investigate	Details of investigation	
		appropriate to determine that the occurrence of the adverse event is due to the subject's condition or factors other than the study drug (such as the underlying disease, complications or concomitant medications), and an association with the study drug can be ruled out

[figure not shown]
# 9.6 Definition of Adverse Drug Reaction

[figure not shown]
Adverse events for which the relationship with the study drug is determined to be "related" will be handled as adverse drug reactions.

### 9.7 Action If an Adverse Event Occurs

#### 9.7.1 Recommended Action for Adverse Events

If an adverse event occurs, the investigator or subinvestigator will take the necessary action, will report it to the sponsor if necessary, and, as far as possible, will observe the course of the adverse event until the subject recovers and the adverse event disappears or is relieved (even after the end of the specified observation period). However, even in a situation where the adverse event does not disappear and is not relieved, if it can be determined that the subject's condition is stable and his safety is ensured, the investigator or subinvestigator will end observation in the study, after providing an explanation to the subject and his legally acceptable representative (however, treatment of the relevant symptoms will continue).

#### 9.7.2 Action If a Serious Adverse Event Occurs

If a serious adverse event occurs, the investigator or subinvestigator will provide appropriate treatment, and also promptly report information about the adverse event to the sponsor, for example by telephone or fax. The investigator will also report the details in writing to the sponsor and the director of the study site. The written report to the director of the study site will be made according to the procedures and format of the relevant medical institution.

will be recorded on the case report form.

#### 10. Other Endpoints

1) Motor function assessment items (lower limbs and upper limbs) Motor function assessment will be performed before the first dose of the study drug in Part 1, before the first dose of the study drug and after the last dose of the study drug (Day 85 to Day 99, or at withdrawal) in Part 2, before the first dose of the study drug, after the 12th dose (Week 12/ Day 84 to Week 13/ Day 85 prior to study drug administration), after the 24th dose (Week 24/ Day 168 to Week 25/ Day 169 prior to study drug administration), after the 36th dose (Week 36/ Day 252 to Week 37/ Day 253 prior to study drug administration), and after the last dose of the study drug (Week 49/ Day 337 to Week 51/ Day 351, or at withdrawal) in Part 2-Extension, and before the first dose of the study drug, after the 12th dose (Week 12/ Day 84 to Week 13/ Day 85 prior to study drug administration), after the 24th dose (Week 24/ Day 168 to Week 25/ Day 169 prior to study drug administration), after the 36th dose (Week 36/ Day 252 to Week 37/ Day 253 prior to study drug administration), and after the last dose of the study drug (Week 49/ Day 337 to Week 51/ Day 351, or at withdrawal) in Part 2-Extension-2. Assessment will be performed twice at each planned time point before the first dose of the study drug and after the last dose of the study drug in Part 1, Part 2, Part 2-Extension, and Part 2-Extension-2, and recorded on the case report form. The maximum values will be used as data. At other planned time points, assessment will be performed once, and will be recorded on the case report form. The measurement procedure for each item will be specified in a separate procedure. Note that measurement of motor function assessment items (upper limbs) will be started when possible, at a timing that suits the subject's schedule.

- 6-minute walk test
   The distance a subject is able to walk in 6 minutes, walking as fast as possible, will be measured.
- Timed Floor to Stand
   The time a subject takes when getting out of floor and standing up as quickly as possible will be measured.
- Timed up and go test
   The time a subject takes to stand up from sitting on a platform (a stool), walk as quickly as possible to a cone 3 m ahead and sit back down on the same platform will be measured.

Time to run/walk 10 m
 The time a subject takes to run or walk 10 m as quickly as possible will be measured.

- North Star Ambulatory Assessment
   Motor functions divided into 17 items, including standing position and walking, will be assessed. A score from 0 points to 2 points will be assigned for each item depending on the subject's function level, and the total point score will be used for assessment.
- Performance of Upper Limb
   Upper limb functions divided into 22 items, covering the regions of the shoulders, elbows and hands, will be assessed. A 3-stage score of 0, 1 or 2 will be assigned for each item, and the total point score will be used for assessment.

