#### 11) Motor function assessment

<Investigation point>

To be performed once each in the period from Week 12/ Day 84 to

Week 13/ Day 85 (pre-dose), the period from Week 24/ Day 168 to

Week 25/ Day 169 (pre-dose), and the period from Week 36/ Day 252 to

Week 37/ Day 253 (pre-dose), and twice in the period from Week 49/ Day 337 to

Week 51/ Day 351.

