# 6.4.5.2 Items to Be Performed During the Treatment Period (Week 1/ Day 1 to Week 48/ Day 336) and Follow-Up Period (Week 49/ Day 337 to Week 52/ Day 358)

The visit window for items performed on Week 2/ Day 8 to Week 50/ Day 344 is ±2 days, and the visit window for items performed on Week 52/ Day 358 is ±7 days. Subjects who complete 48 weeks of study drug administration in Part 2-Extension-2 and complete efficacy assessment after administration may participate in the long-term extension study. For subjects who participate in the long-term extension study, Week 52/ Day 358 will not be performed.

As a measure to prevent the spread of the novel coronavirus, self-administration will be allowed. Consent for self-administration will be obtained from the legally acceptable representative, and the guardian performing self-administration will be given training in the method of storing the study drug and the method of administering the study drug before self-administration starts.

- 1) Administration status of the study drug
  - Whether the study drug was administered, date/time of study drug administration, dose level, actual dose (mg), and checking the "Self-Injection Diary" if self-administration was performed
  - <Time points at which self-administration is possible>
  - Week 28/ Day 190, Week 30/ Day 204, Week 31/ Day 211, Week 32/ Day 218,
  - Week 34/ Day 232, Week 35/ Day 239, Week 36/ Day 246, Week 38/ Day 260,
  - Week 39/ Day 267, Week 40/ Day 274, Week 42/ Day 288, Week 43/ Day 295,
  - Week 44/ Day 302, Week 46/ Day 316, Week 47/ Day 323
- 2) Investigating concomitant medications and concomitant therapy
- 3) Investigating adverse events
- 4) Height and body weight
  - <Observation point>

\*13: To be performed twice.

Week 13/ Day 85, Week 25/ Day 169, Week 37/ Day 253, Week 48/ Day 330

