#### 12) Motor function assessment (lower limbs)

<Investigation point>

To be performed once each in the period from Week 12/ Day 84 to Week 13/ Day 85 (pre-dose), the period from Week 24/ Day 168 to Week 25/ Day 169 (pre-dose), and the period from Week 36/ Day 252 to Week 37/ Day 253 (pre-dose), and performed twice in the period from Week 49/ Day 337 to Week 51/ Day 351.

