#### 16) Quantitative muscle strength assessment

<Investigation point>

To be performed once each in the period from Week 12/ Day 84 to

Week 13/ Day 85 (pre-dose), the period from Week 24/ Day 168 to

Week 25/ Day 169 (pre-dose), and the period from Week 36/ Day 252 to

Week 37/ Day 253 (pre-dose), and performed twice in the period from

Week 49/ Day 337 to Week 51/ Day 351.

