# 11.4.4.5

#### 11.4.5 Analysis Methods for Other Items

# 11.4.5.1 Motor Function Assessment Items (Lower Limbs and Upper Limbs)

For the following endpoints, summary statistics will be calculated for the measurement at each time point and the change from before the first dose of the study drug. A listing by subject and time course plot will also be prepared. For the 6-minute walk test, the ratios of measured values to expected values will be calculated and analyzed in the same way as measured values.

- 6-minute walk test
- Timed Floor to Stand
- Timed up and go test
- Time to run/walk 10 m

- North Star Ambulatory Assessment
- Performance of Upper Limb

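### In both extensions, changes in lower-limb motor function and muscle strength to Weeks 12, 24 and 36 compare one assessment with the maximum of two (minor, descriptive endpoints)

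*Combined protocol and SAP*

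**What the plan says.** **Rule for the data value.** Section 10, item 1 (motor function), says: "Assessment will be performed twice at each planned time point before the first dose of the study drug and after the last dose", and names all four study parts. It continues: "The maximum values will be used as data. At other planned time points, assessment will be performed once". Section 10, item 4 (muscle strength), has the same rule but names only Part 1, Part 2 and Part 2-Extension.

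**Two assessments before dosing.** For boys entering the study, the footnote to motor function and strength in Section 6.4.1 reads: "To be performed twice, at least 28 days after muscle biopsy". For boys continuing into an extension, Sections 6.4.4.1 and 6.4.5.1 carry a footnote to both items; the one for Part 2-Extension-2 reads: "To be performed twice".

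**One assessment at the interim visits.** For Part 2-Extension, Section 6.4.4.2 says of motor function: "To be performed once each in the period from Week 12/ Day 84 to" Week 13 before dosing, and likewise around Weeks 24 and 36. Strength follows the same schedule. Section 6.4.5.2 repeats this for Part 2-Extension-2, except that upper-limb function has no Week 12 visit and starts only when it can be arranged.

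**Two assessments at the end.** In Part 2-Extension-2, lower-limb function is done once at each interim visit "and performed twice in the period from Week 49/ Day 337 to Week 51/ Day 351". Strength has the same pattern: "Week 37/ Day 253 (pre-dose), and performed twice in the period from" Week 49 to Week 51.

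**Analysis.** Section 11.4.5.1 states that "summary statistics will be calculated for the measurement at each time point and the change from before the first dose of the study drug". Section 11.4.5.4 says the same for strength. Both add listings by subject and time-course plots. Neither gives a rule that aligns a single assessment with a maximum of two.

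**The concern.** The larger of two noisy readings is on average higher than a single reading. If the baseline is a maximum of two and the follow-up is one reading, the change is pushed downwards even when nothing has happened. More boys would not average this out, and the study has no control group to absorb it.

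For 6-minute walk distance and strength, a stable boy would on average seem to lose ground through Week 36. When the maximum of two returns after the last dose, he would seem to regain it. That step would show in the summary statistics by time point as well as in the listings and plots. For motor function it applies in both extensions. For strength it applies in Part 2-Extension, as far as those visits took place given that dosing there was temporarily discontinued; in Part 2-Extension-2 it depends on how Section 10, item 4, is read.

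Two drafting points sit alongside:

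- The single word *maximum* in item 1 also governs three timed tests: Timed Floor to Stand, timed up and go, and 10 m run/walk. Read literally, it keeps the slower run.
- Item 4 leaves Part 2-Extension-2 out of the two-assessment rule, while Sections 6.4.5.1 and 6.4.5.2 schedule two.

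**Working it through.** The plan states no figure on this point, so there is none to reproduce.

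**Inputs**
- Assessments: two before the first dose (maximum used) and one at Weeks 12, 24 and 36 (Sections 10, 6.4.1, 6.4.4 and 6.4.5).
- Boys: 3 per dose level, 6 per part (Section 11.7). Sections 11.4.5.1 and 11.4.5.4 do not say whether summaries are by dose, so both numbers are used.
- Assessment-to-assessment SD, written s: not in the documents. Assumed 10 to 40 m for the 6-minute walk and 0.3 to 1.0 s for timed tests.

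**Step 1: shift with no true change.** For two independent normal assessments with the same mean, E[max] - mean = s/√π = 0.564 s. So E[single - max of two] = -0.564 s. A simulation of 2,000,000 draws gave -0.566 s, with the single reading lower in 66.7% of draws. Maximum minus maximum gave -0.001 s, which is simulation error around zero.

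**Step 2: against the standard error.** Var(max of two) = s²(1 - 1/π), so the change has variance s²(2 - 1/π).
- 3 boys: SE = √((2 - 1/π)/3) s = 0.749 s; ratio 0.564/0.749 = 0.75.
- 6 boys pooled: SE = √((2 - 1/π)/6) s = 0.529 s; ratio 0.564/0.529 = 1.07.

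**Step 3: departures from exchangeability, 3 boys**

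| Assumption | Shift | SE | Ratio |
|---|---|---|---|
| The two assessments correlate at 0.5 (s is then the total within-subject SD) | √(0.5/π) = 0.399 s | 0.783 s | 0.51 |
| True changes vary between boys with SD 1 s | 0.564 s | 0.946 s | 0.60 |
| True changes vary between boys with SD 2 s | 0.564 s | 1.376 s | 0.41 |
| Second assessment 0.5 s lower, not carried over | 0.349 s | 0.753 s | 0.46 |
| Second assessment 0.5 s higher, not carried over | 0.849 s | 0.753 s | 1.13 |

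The last two rows use d·Φ(d/√2) + √2·φ(d/√2), with d = -0.5 and +0.5.

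**Step 4: in units, on the assumed SDs**
- 6-minute walk: 0.564 × 10 = 5.6 m to 0.564 × 40 = 22.6 m.
- Timed tests: 0.564 × 0.3 = 0.17 s to 0.564 × 1.0 = 0.56 s. This is an apparent gain if the slower run is kept before dosing, and an apparent slowing if the faster one is kept.
- Slower minus faster of two runs: 2/√π = 1.128 s on average, so 0.34 to 1.13 seconds.

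**Step 5: mean of two before dosing instead.** The shift is 0 for exchangeable assessments. SE for 3 boys = √(1.5/3) s = 0.707 s, against 0.749 s now; at correlation 0.5 it is 0.764 s against 0.783 s. If the second assessment differs by 0.5 s, up to 0.5/2 = 0.25 s remains.

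**Step 6: comparisons that are matched.** Motor change to end of treatment is maximum against maximum in every part. Part 2 has no interim motor or strength visit (Section 6.4.3.2).

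**The case against.** The strongest reply is that little depends on this. These are *other* endpoints. Section 11.1 says that the analysis is descriptive and without tests, no decision rule uses them, and listings by subject are planned. For distance and strength the shift runs against the drug, so it cannot create apparent benefit there. Section 11 announces a separate SAP, Section 11.3 a data handling standard and Section 10 separate measurement procedures. None of these is available here, and any could already hold an alignment rule. A footnote giving the number of assessments per visit would disclose the issue without a second baseline. All of this stands and keeps the point minor, although a footnote discloses the shift without removing it.

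A reader might also infer more than the documents support:

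- *That 0.75 of a standard error is a ceiling.* It is the exchangeable case for 3 boys. Step 3 gives values on both sides, and pooling 6 boys gives 1.07.
- *That the walk shift could reach 0.849 × 40 = 34 m.* That requires a practice gain at the second assessment to be wholly lost by Week 12. If it carries over, the shift is 0.849 - 0.5 = 0.349 SD. The boys repeat these tests before each part from Part 2 on, so carry-over is plausible.
- *That all motor items are affected alike.* Upper-limb function may have no pre-dose value in continuing boys. North Star and Performance of Upper Limb are bounded scores, to which the normal-theory figure is not applied.
- *That both assessments fall in one visit.* The documents give only a window, so the correlation of 0.5 is an assumption.
- *That the plan intends to keep the slower run.* The timed tests are done as fast as possible, which fits best performance; only the literal wording says otherwise.
- *That strength in Part 2-Extension-2 is certainly affected.* If item 4 is read literally and baseline is taken within that part, Weeks 12 to 36 compare one with one. The schedule of two suggests a drafting omission. With a baseline before the first dose in the study, boys who entered earlier have a two-assessment baseline on every reading.

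**Conclusion.** The concern holds as a minor point. Under the visible rules, the planned changes in lower-limb motor function and strength to Weeks 12, 24 and 36 of the extensions are not like with like. For upper-limb function this applies at Weeks 24 and 36 where a pre-dose value exists. The direction follows from the rule; the size depends on an SD that the documents do not give, and on roughly normal, exchangeable assessments. On that basis the shift is a little over half an assessment-to-assessment SD, comparable with the standard error of these very small groups. Correlated assessments or varying true changes make it smaller relative to that error.

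The documents do not support extending this to the motor change at end of treatment or to Part 2, and the dystrophin endpoints are not involved. For strength in Part 2-Extension-2, the end-of-treatment shift is either 0 or -0.564 SD until Section 10, item 4, is reconciled with the schedule.

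**What to change.** 1. For changes to Weeks 12, 24 and 36 and for time-course plots, use the mean of the two recorded assessments wherever two were made.
2. If best performance is kept for the end-of-treatment change, state maximum for distance, score and force and minimum for times, and label the two baselines.
3. Reconcile Section 10, item 4, with the two strength assessments scheduled for Part 2-Extension-2 in Sections 6.4.5.1 and 6.4.5.2.
4. If the separate SAP or a measurement procedure already sets such a rule, align Section 10 with it instead.

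**Cost.** No new data or visits are needed, because both assessments go on the case report form, and precision improves slightly. Against that, there are two labelled baselines, and a residual of up to about 0.25 SD if practice or fatigue between assessments is 0.5 SD. The change must be documented under Section 11.5 and, because Section 10 is edited, under Section 15.7. Section 1.2.6 shows Part 2 complete and Part 2-Extension-2 in progress, so the record should say that the change was made after Part 2 data existed.
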